4.4 Per-protocol Analysis Set

The Per-protocol Analysis Set will consist of those subjects in the ITT Analysis Set without any protocol deviations which could potentially have a substantial impact on the primary efficacy outcome. The precise reasons for excluding subjects from the Per-protocol Analysis Set will be fully defined and documented prior to the clinical database lock. Subjects will be analyzed based on their randomized treatment.

4.5 Open-label Pharmacokinetic Analysis Set

The Open-label Pharmacokinetic (PK) Analysis Set includes all subjects who have at least one measurable pimavanserin plasma concentration collected in the open-label period.

4.6 Double-blind Pharmacokinetic Analysis Set

The Double-blind PK Analysis Set includes all subjects who have at least one measurable pimavanserin plasma concentration collected in the double-blind period.

5 DATA HANDLING CONVENTIONS

All data collected in the study will be listed.

5.1 General Data Reporting Conventions

In general, listings will be sorted by randomized treatment group (placebo, pimavanserin), enrolled but not randomized, screen failure (screened but not enrolled), and subject ID, and all relevant data will be presented. Data from screen failures will be included in listings where available.

For continuous variables, the following summary statistics will be provided: number of subjects, mean, standard error of the mean (SE), standard deviation (SD), minimum, maximum, and median. For pharmacokinetic data, the geometric mean will also be provided. Unless specified otherwise, means, medians, and confidence intervals (CIs) will be presented to one more decimal place than the raw data, and the standard deviations and standard errors will be presented to 2 more decimal places than the raw data.

For categorical variables, summaries will include the number and percentage of subjects in each category, using the number of subjects with non-missing values as the denominator for

the percentages (unless otherwise specified). Categories with zero counts will not have zero percentages displayed. Percentages will be presented to 1 decimal place.

Unless specified otherwise, all statistical tests will be 2-sided hypothesis tests and all CIs will be 2-sided 95% CIs. Two-sided P-values will generally be presented to 4 decimal places; values less than 0.0001 will be presented as <0.0001.

When converting number of days to months, it will be calculated as the number of days divided by 365.25 and then multiplied by 12. When converting number of days to years, it will be calculated as the number of days divided by 365.25.

5.1.1 Open-label Period

In general, dates associated with open-label data will be accompanied on the listings by the study day relative to the date of first dose of open-label pimavanserin. Open-label study day 1 is the date of first dose of open-label pimavanserin.

For assessments occurring on or after the open-label study day 1, open-label study day is calculated for a given subject as

$$\text{assessment date} - \text{first open-label dose date} + 1.$$

For assessments occurring prior to the open-label study day 1, open-label study day is calculated for a given subject as

$$\text{assessment date} - \text{first open-label dose date}.$$

Unless specified otherwise, the following summaries will be provided:

1. all subjects combined;
2. by randomization status (not randomized and randomized);
3. by final dose level (20 and 34 mg) of open-label pimavanserin administered during the open-label period.

5.1.2 Double-blind Period

In general, dates associated with double-blind data points will be accompanied on the listings by the study day relative to the date of first dose of double-blind study drug. Double-blind study day 1 is the date of first dose of double-blind study drug.

For assessments occurring on or after the double-blind study day 1, double-blind study day is calculated for a given subject as

$$\text{assessment date} - \text{first double-blind dose date} + 1.$$

For assessments occurring prior to the double-blind study day 1, double-blind study day is calculated for a given subject as

$$\text{assessment date} - \text{first double-blind dose date}.$$

Unless specified otherwise, the following summaries will be provided:

1. by treatment group (placebo and pimavanserin);
2. by dose level (20 and 34 mg) of double-blind pimavanserin administered during the double-blind period for the pimavanserin group.

5.2 Derived Variables

In general, the total scores and subscores for assessment scales will be derived within the analysis datasets. In the event that total scores and/or subscores are also collected on the electronic case report form (eCRF), the derived values will be used for all analyses. Both the raw and derived scores will be presented in listings.

5.2.1 Open-label Baseline

Open-Label Baseline is defined as the last non-missing assessment, including those from repeated and unscheduled measurements, before the date of first dose of open-label pimavanserin.

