3.3 Open-label Period (12 Weeks)

During the open-label period, eligible subjects will begin receiving pimavanserin 34 mg once daily (QD) beginning at Week 0 (open-label Baseline). Subsequent clinic visits will occur at Weeks 2, 4, 8, and 12. Dose adjustments are permitted at scheduled or unscheduled visits until Week 4. After Week 4, the subject's dose will remain fixed at either 34 mg or 20 mg once daily.

To enter the double-blind period, eligible subjects must meet the following response criteria at Weeks 8 and 12:

- Subject experiences a $\geq 30\%$ reduction (improvement) from Week 0 (open-label Baseline) on the SAPS-H+D Total Score AND
- Subject has a CGI-I score of 1 (very much improved) or 2 (much improved), relative to Week 0 (open-label Baseline)

A subject who does not meet response criteria at Weeks 8 and 12 will be withdrawn from study drug and enter the safety follow-up period of the study.

Pharmacokinetic samples will be collected at Weeks 0, 8, and 12. Pharmacokinetic samples will also be collected, if possible, at any ET visit or the visit immediately following any SAE or following an AE leading to discontinuation.

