5.1.3 Dosing and Administration

The first dose of study drug will be administered at the clinic; study drug kits will then be dispensed to the subject to take home. Each daily dose consists of 2 individual tablets that should be taken together. Subjects should be instructed to take 2 whole tablets, orally, once each day. Subjects should be instructed to not crush the tablets. The tablets may be taken with or without food.

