5.1.4 Dose Adjustments/Modifications/Delays

The first dose of open-label pimavanserin 34 mg will be taken at the beginning of the open-label period (Week 0 [Visit 2]). Pimavanserin will continue daily at this dose level for at least the first week of treatment. After the first week, if the subject is unable to tolerate the 34 mg dose, the dose may be decreased to 20 mg at any study visit (scheduled or unscheduled) until Week 4 (Visit 4). If the dose is decreased to 20 mg it may later be increased to 34 mg based on investigator judgment at any study visit (scheduled or unscheduled) until Week 4 (Visit 4). After Week 4 (Visit 4), the dose of study drug will remain fixed at either 34 mg or 20 mg once daily.

When the dose is adjusted, subjects should be instructed to return all treatment kits, blister cards, and unused tablets from the previous dose level before the next dose level is dispensed. Dose adjustments will be recorded in the interactive response technology (IRT) system.

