5.3 Analysis Visit Windows

5.3.1 Open-label Period

Efficacy, safety and pharmacokinetic assessments for the open-label (OL) period will be summarized by analysis visit as presented in [Table 3](#). For exploratory efficacy endpoints and MMSE, assessments more than 14 days after last dose of study drug will be assigned an analysis visit but will not be selected for the by-visit analyses.

Table 3 Analysis Visit Windows for the Open-label Period

Study Visit	Analysis Visit	Target OL Study Day ^a	Study Day Interval
Week 0	OL Baseline	1	≤1
Week 2	OL Week 2	15	2 to 21
Week 4	OL Week 4	29	22 to 42
Week 8	OL Week 8	57	43 to 70
Week 12	OL Week 12	85	71 to 98 (or day of first dose of double-blind study drug ^b)

^aDerivation of open-label study day is described in [Section 5.1.1](#). Open-label study day 1 is the date of first dose of open-label pimavanserin.

^bFor subjects who are randomized in the double-blind period.

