14.1 Adverse Events

All Adverse events (AEs) will be coded using MedDRA version 20.0 or newer.

An AE (classified by preferred term) will be considered a treatment emergent AE (TEAE) if the onset date was on or after the date of first dose of open-label pimavanserin and up to 30 days past the last dose of study drug. AEs reported on Day 1 based on open-label Baseline (pre-dose) findings (e.g. clinically significantly abnormal vital signs, laboratory test results, or electrocardiogram parameters) will not be considered as TEAEs.

Each TEAE will be assigned to either the open-label or double-blind period based on the onset date. For randomized subjects, if the onset date was on or after the date of first dose of double-blind study drug, the TEAE will be assigned to the double-blind period. All other TEAE will be assigned to the open label period.

The event counts and the number and percentage of subjects reporting TEAEs will be tabulated by SOC and preferred term; and, by SOC, preferred term, and maximum severity. If more than 1 AE occurs with the same preferred term for the same subject, the subject will be counted only once for that preferred term using the most severe occurrence for the

summarization by severity. In addition, the event counts and the number and percentage of subjects with TEAEs classified by the Investigators as related to the study drug, with most frequently reported TEAEs (preferred terms reported by $\geq 5\%$ of subjects overall for the open-label period and $\geq 5\%$ of subjects in either treatment group for the double-blind treatment period), with treatment emergent serious AEs, with fatal AEs (i.e. events that cause death), and with TEAEs leading to discontinuation of study drug will be summarized by SOC and preferred term. The display in these tables will be sorted alphabetically by SOC and then by descending subject frequency for the preferred terms using combined counts from both groups within each SOC. The event counts and the number and percentage of subjects with any TEAEs will also be tabulated by preferred term without SOCs. This table will be sorted by descending subject frequency using combined counts from all subjects.

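### SAP 5.2.1 sets open-label Baseline strictly before the first-dose date, which excludes the Week 0 values that SAP Table 3 and SAP 14.1 treat as Baseline

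*SAP*

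**What the plan says.** SAP 5.2.1 takes as open-label Baseline the last non-missing assessment, "including those from repeated and unscheduled measurements, before the date of first dose of open-label pimavanserin". The cut-off is the calendar date of dosing, not the time of the dose.

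Other places put Baseline on that date:

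- **SAP 5.3.1, Table 3** assigns Week 0 to the OL Baseline analysis visit, with target day 1 and an interval of day 1 or earlier. Its footnote says "Open-label study day 1 is the date of first dose of open-label pimavanserin".
- **SAP 14.1** refers to "AEs reported on Day 1 based on open-label Baseline (pre-dose) findings", so pre-dose Day 1 findings count as Baseline findings.
- **Protocol 3.3** measures response "from Week 0 (open-label Baseline) on the SAPS-H+D Total Score", which equates Week 0 with open-label Baseline.
- **Protocol 5.1.4** places the first open-label dose at Week 0 (Visit 2), and Protocol 5.1.3 adds "The first dose of study drug will be administered at the clinic".

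The neighbouring definition, SAP 5.2.2, includes the dosing date for double-blind Baseline. It concerns a different baseline, so it is a contrast and not a contradiction. The SAP does not say whether 5.2.1 or Table 3 prevails.

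**The concern.** The notes to Protocol Table S-1 ask sites to complete each visit in one day where possible. The ordinary subject is therefore assessed and dosed on the same date, and 5.2.1 discards exactly those assessments. Two groups of measures are affected differently.

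**(a) Not scheduled at Screening:** ZBI, KSS, EQ-5D-5L/VAS and ESRS-A. These normally have no earlier value, so their open-label Baseline, and every change from it, would be missing.

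**(b) Also taken at Screening:** SAPS-H+D, CGI-S, MMSE, vital signs, ECG and laboratory tests. These would take an earlier value, usually from Screening and possibly from before a washout under inclusion criterion 14. The tables would fill normally with a different reference behind them. This reaches:

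- the open-label change and shift tables;
- change from open-label Baseline in the double-blind safety set, including QTcF change categories (SAP 14.4.2) and MMSE (14.7.2);
- the change-based criteria for weight (Table 7) and QTcF (Table 8);
- the SAPS-H+D part of the responder summary (13.3.7);
- the OL Baseline MMSE subgroup (12.5.1), which is used for the primary and key secondary endpoints.

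In 13.3.7 the CGI-I part stays scored relative to Visit 2 (Protocol Table S-1, footnote e), so one composite would have two reference dates. For ECG, a fallback to Visit 1 replaces the single Week 0 tracing with the mean of the Screening triplicate (SAP 5.3.4).

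**Working it through.** This is a check of date logic; no sample-size, power or alpha figure is involved.

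**Step 1. Which days qualify.** Under SAP 5.1.1, study day = assessment date − first-dose date + 1 on or after the dosing date, and the same difference without the +1 before it. There is no day 0.

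| Days from first-dose date | Study day | Qualifies under 5.2.1 (before the date) | Qualifies under Table 3 (day ≤ 1) |
|---|---|---|---|
| −35 | −35 | yes | yes |
| −3 | −3 | yes | yes |
| −1 | −1 | yes | yes |
| 0 | 1 | **no** | **yes** |
| +1 | 2 | no | no |

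The rules differ only on Day 1, the day of the Week 0 visit. Including the dosing date makes them agree.

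**Step 2. Measures left without a Baseline.** In Protocol Table S-1 and SAP Table 1, four instruments are marked at Week 0 but not at Screening: ZBI, KSS, EQ-5D-5L and ESRS-A. What cannot be derived for same-day subjects is:

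- change scores in five instrument sections: 13.3.8 (ZBI), 13.3.9 (KSS), 13.3.11 (EQ-5D VAS), 14.8.1 and 14.8.2 (ESRS-A change from open-label Baseline). SAP 13.3.2 asks for the ZBI, KSS and EQ-5D VAS changes again;
- the open-label Pareto classification in 13.3.13;
- three open-label Baseline characteristics in 8.2: ZBI, KSS and EQ-5D VAS.

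Observed by-visit summaries survive, because SAP 5.3.1 says "assessments for the open-label (OL) period will be summarized by analysis visit as presented in" Table 3. This includes all of 13.3.12.

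**Step 3. Length of the change interval for measures that fall back.** Assume the earlier value is the Visit 1 value. The screening period is 3 to 35 days (Protocol 3.2).

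- Nominal Week 12 is day 85, so 85 − 1 = 84 days from Week 0. From Visit 1: 84 + 3 = 87 to 84 + 35 = 119 days.
- With the +7-day visit window, 84 to 91 days from Week 0. From Visit 1: 84 + 3 = 87 to 91 + 35 = 126 days.
- With the Table 3 window of days 71 to 98, 70 to 97 days from Week 0. From Visit 1: 70 + 3 = 73 to 97 + 35 = 132 days. For randomized subjects Table 3 also allows this window to end on the day of the first double-blind dose.

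If the earlier value is a repeat or unscheduled one, the extra gap can be as short as 1 day.

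**Step 4. Effect on the 30% criterion in 13.3.7.** A reduction of at least 30% means a score of at most 0.7 × reference. The cut-off therefore moves 0.7 points for each point by which the two references differ, in either direction. As an illustration at the entry floor (total score of at least 10 at both visits, inclusion criterion 8), take a Week 0 score of 10. The Screening score of 12 and the later score of 8 are assumptions.

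- Reference 10: 0.7 × 10 = 7, so the highest qualifying score is 7. A later score of 8 is (10 − 8)/10 = 20.0%, not a response.
- Reference 12: 0.7 × 12 = 8.4, so the highest qualifying score is 8. A later score of 8 is (12 − 8)/12 = 33.3%, a response.

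**The case against.** The strongest reply is that the intent is obvious. Table 3, 14.1 and the instrument descriptions in 5.2 all treat Week 0 as Baseline, and the contrast with 5.2.2 suggests a wording slip. A programmer who applied 5.2.1 to everything would find ZBI, KSS, EQ-5D and ESRS-A almost without Baseline values, and that would expose the rule before reporting. The 13.3.7 count of responders at both Weeks 8 and 12 could also disagree with who was randomized. On this view the point is editorial.

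Much of that stands. The intent is clear, and the visible gaps in group (a) would probably reveal the error, which lowers the risk of a silent shift in group (b). It does not remove the conflict. SAP 5.2.1 is the operative definition, the SAP gives nothing that overrides it, and following it as written produces wrong or missing outputs.

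A second reply is that one term is being read two ways: by Table 3 for observed Baseline rows and by 5.2.1 for change scores. That follows from the SAP having two rules. The by-visit summaries are tied expressly to Table 3. The characteristics in 8.2 and the classification in 13.3.13 are not by-visit observed summaries, so 5.2.1 is the reasonable rule for them.

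A third reply is that a pre-dose limit appears in neither Table 3 nor 5.2.2. That is correct; its only support is 14.1.

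**Conclusion.** The concern holds. SAP 5.2.1 contradicts Table 3 and 14.1 and is wrong as written. It should be fixed before open-label Baseline is derived.

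The disagreement is one study day, but it is the day on which most subjects' Week 0 data fall. For subjects assessed and dosed on the same date, four instruments lose their open-label Baseline and the group (b) measures take an earlier reference. Values from a split visit on an earlier day would still qualify under 5.2.1.

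The intervals in Step 3 rest on the fallback being the Visit 1 value, and the SAPS-H+D example rests on assumed scores. The documents do not give what is needed to state the net size or direction for the trial.

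Not affected: randomization; the overall primary, key secondary and interim analyses; double-blind efficacy change scores; and observed by-visit summaries. Most affected outputs are descriptive.

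**What to change.** In SAP 5.2.1, replace *before the date* with *on or before the date* of the first open-label dose, and limit it to pre-dose values. Scheduled Visit 2 assessments can be taken as pre-dose unless known otherwise. Including the dosing date is enough to align 5.2.1 with Table 3 and with the convention in 5.2.2. The pre-dose limit is an addition that follows 14.1, and the default for Visit 2 assessments is a practical suggestion not found in the documents.

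The cost is one SAP definition and at most a minor programming update, with no new data collection.

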5.2.2 Double-blind Baseline

Double-Blind Baseline is defined as the last non-missing assessment, including those from repeated and unscheduled measurements, on or before the date of first dose of double-blind study drug.

5.2.3 Time from Randomization to Relapse in the Double-blind Period

For subjects who experience a relapse event, the time to relapse will be calculated as

$$\text{date of relapse} - \text{date of randomization} + 1.$$

For the primary efficacy endpoint the date of relapse is determined by the IAC.

Subjects who complete the 26-week double-blind period, those who discontinue early, and those who are ongoing at the time of the applicable analysis cutoff, without experiencing a relapse event, will be censored at the time of the last applicable SAPS-H+D assessment. See [Section 13.1](#) for further details regarding the analysis cutoffs, and [Section 13.2.2](#) for censoring times for sensitivity analyses. The censored follow-up time will be calculated as:

$$\text{date of last applicable SAPS-H+D assessment} - \text{date of randomization} + 1.$$

Subjects who have not experienced a relapse event and do not have any post-baseline SAPS-H+D assessments in the double-blind period, will be censored at the time of randomization. The censored follow-up time will have a value of 1 day.

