- h A separate informed consent (and assent, if applicable) must be given for the pharmacogenomic component of the study. This consent may be obtained at any time during the study. If informed consent is given in time for sample collection at Visit 2, a pre-dose sample should be collected at Visit 2. If informed consent for pharmacogenomics is not given in time for sample collection at Visit 2, a sample may be collected any time after informed consent for pharmacogenomics is given.
- i Blinded study drug will be dispensed after randomization at Visit 6 (Week 12).

Table S–2 Schedule of Assessments for ACP-103-045: Double-blind Period

Visit week	13	14	16	18	20	22	24	26	30	34	38/EOT	42
Allowable visit window (# days)	±3	±3	±3	±3	±3	±3	±3	±3	±7	±7	+7	+3
Visit Number	7	8	9	10	11	12	13	14	15	16	17/ET	18
Visit Type (Clinic [C] or Telephone [T])	C	C	C	C	T	C	T	C	C	C	C	T
Mini-Mental State Examination	X	X	X	X		X		X	X	X	X	
Physical and neurological examinations						X					X	
Vital signs and weight	X	X	X	X		X		X	X	X	X	
12-lead electrocardiogram				X				X			X	
Clinical laboratory tests				X				X			X	
Pregnancy test ^a								X			X	
SAPS-H+D	X	X	X	X		X		X	X	X	X	
Clinical Global Impression-Improvement ^b	X	X	X	X		X		X	X	X	X	
Clinical Global Impression-Severity	X	X	X	X		X		X	X	X	X	
Zarit Burden Interview ^c				X				X			X	
Karolinska Sleepiness Scale				X				X			X	
EQ-5D-5L				X				X			X	
Assessment for protocol-defined relapse criteria	X	X	X	X	X	X	X	X	X	X	X	
Assessment for concomitant medications	X	X	X	X	X	X	X	X	X	X	X	X
Global Clinician Assessment of Suicidality	X	X	X	X	X	X	X	X	X	X	X	
Extrapyramidal Symptom Rating Scale A	X	X	X	X		X		X	X	X	X	
Assessment for adverse events	X	X	X	X	X	X	X	X	X	X	X	X
Pharmacokinetic sample collection ^d	X					X					X	
Drug dispensation		X	X	X		X		X	X	X		
Drug return and accountability	X ^e	X	X	X		X		X	X	X	X	

Footnotes and abbreviations for Table S-2 on next page

Abbreviations: EOT=end-of-treatment; ET=early termination; SAPS-H+D=Scale for the Assessment of Positive Symptoms, Hallucinations and Delusions subscales

For additional details on study procedures, see [Section 6](#).

Note: All efforts should be made to complete each visit in a single day. In the event of a split visit, the CGI-S/CGI-I and the SAPS H+D must be completed on the same day.

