9.5.1 Primary Efficacy Analyses

The time from randomization to relapse in the double-blind period will be compared between treatment groups using a Cox regression model with effects for treatment group, dementia subtype, and region. The nominal p-value, hazard ratio, and 95% confidence interval will be reported. Subjects who discontinue early or complete the study without having experienced a

relapse event will be censored at the time of last assessment for relapse. The primary analysis will be based on adjudicated relapse events ([Section 9.5.7](#)).

A sensitivity analysis will be performed based on the Investigator assessment of relapse. Additional sensitivity analyses to assess the potential impact of informative censoring will be specified in the Statistical Analysis Plan.

Kaplan-Meier curves of time from randomization to relapse will be presented for each treatment group. In addition, Kaplan-Meier estimates of the proportion of subjects who relapse along with pointwise 95% confidence intervals will be provided for the 26-week double-blind period.

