5.2.5 Scale for the Assessment of Positive Symptoms-Hallucinations + Delusions

The Scale for the Assessment of Positive Symptoms-Hallucinations + Delusions (SAPS-H+D) is assessed at Screening, Baseline (Week 0), and Weeks 2, 4, 8, and 12 during the open-label period, and at Weeks 13, 14, 16, 18, 22, 26, 30, 34, and 38 during the double-blind period.

The SAPS was designed to measure positive psychotic symptoms. Positive symptoms include hallucinations, delusions, abnormalities in language and behavior, and disordered thought processes. The SAPS-H+D subscales will be administered in this study. The Hallucinations and Delusions subscales consist of 20 items, including 2 global ratings of severity for hallucinations (H7) and delusions (D13). Each of the 20 items is scored on a 6-point scale (0=none, 1=questionable, 2=mild, 3=moderate, 4=marked, 5=severe). The SAPS-H+D total score is the sum of the 20 item scores with a possible range of 0 to 100. Higher scores denote more severe symptoms. The hallucinations score (SAPS-H) is the sum of the 7 hallucinations item scores and the delusions score (SAPS-D) is the sum of the 13 delusions item scores.

Missing SAPS-H+D item scores will not be imputed. The total score will be missing if any item score is missing. Similarly, the SAPS-H and SAPS-D scores will be missing if any component item score is missing.

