13.1.1 Deviations From Non-Informative Censoring

One of the assumptions underlying the primary analysis is that the censoring mechanism is non-informative. In order to assess the sensitivity of the primary analysis to deviations from this assumption, a reference-based multiple imputation method will be used (Lu et. al., 2015). Subjects who don't relapse but who discontinue from the study prior to the Week 26 assessment, for any reason other than termination of the study by the sponsor, will have time to relapse values imputed conditionally on their observed censored values. Censoring due to completion of the 26 week double-blind period, study being terminated by the sponsor or ongoing at the time of the interim analysis datacut (for the interim analysis only), will be treated as non-informative and no imputation will be performed for these subjects. The

imputation algorithm will be based on the assumption that the risk of relapse (i.e. hazard rate) for pimavanserin subjects who prematurely discontinue is the same as that for placebo subjects. If the imputed event time exceeds the applicable cutoff date for a planned analysis, or the date corresponding to Week 26 for the subject, whichever comes first, the time-to-event will be right censored at the earlier of the two dates. Random number seeds of 201938 and 202075 will be used for the posterior draw of model parameters from the imputation model and for imputation of censored event times, respectively. A total of 1000 imputed datasets will be created.

The imputation model will be a Cox regression model with piecewise exponential baseline hazards fit to the ITT Analysis Set with treatment, designated dementia subtype, and region as covariates. A noninformative improper prior for the baseline hazard parameters and an improper uniform prior for the regression coefficients will be assumed. For the piecewise constant baseline hazards, the post-baseline follow-up time axis will be partitioned into 2 disjoint intervals, where the interval cut-points will be such that there will be a similar amount of relapse events in each interval. Sampling of model parameters will set the burn-in to 200 and every 10th sample will be kept. [REDACTED]

[REDACTED]

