13.1.2 Sensitivity Analyses

If the study is stopped at the interim analysis, the following sensitivity analyses will be performed:

- Time to relapse based on adjudicated relapse events using data collected up to the study discontinuation date (ITT analysis set). Subjects without any such relapse event will be censored at the last SAPS-H+D assessment prior to the study discontinuation date.
- Time to relapse based on adjudicated relapse events occurring up to the study discontinuation date, plus any additional investigator determined relapse events that occur after the study discontinuation date (ITT analysis set). Subjects without any such relapse event will be censored at the last SAPS-H+D assessment.
- Time to relapse based on investigator determined relapse events using data collected up to the study discontinuation date (ITT analysis set). Subjects without any such relapse event will be censored at the last SAPS-H+D assessment prior to the study discontinuation date.
- Time to relapse based on adjudicated relapse events using the interim analysis dataset and using the Per-protocol analysis set. Subjects without any such relapse event will be censored at the last SAPS-H+D assessment.

If the study is not stopped at the interim analysis, the following sensitivity analyses will be performed:

- Time to relapse based on adjudicated relapse events occurring up to the study discontinuation date, plus any additional investigator determined relapse events that occur after the study discontinuation date (ITT analysis set). Subjects without any such relapse event will be censored at the last SAPS-H+D assessment.

- Time to relapse based on investigator determined relapse events using data collected up to the study discontinuation date (ITT analysis set). Subjects without any such relapse event will be censored at the last SAPS-H+D assessment prior to the study discontinuation date.
- Time to relapse based on adjudicated relapse events occurring up to the study discontinuation date using the Per-protocol analysis set. Subjects without any such relapse event will be censored at the last SAPS-H+D assessment prior to the study discontinuation date.

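### Does SAP 20 need correcting because the SAP censors at the last SAPS-H+D instead of the last relapse assessment, and omits ESRS-A subscale summaries?

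*SAP*

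**What the plan says.** **Censoring of the primary endpoint.** Protocol 9.5.1, like the synopsis, provides that a subject who leaves or finishes without a "relapse event will be censored at the time of last assessment for relapse". Table S-2 has a row headed "Assessment for protocol-defined relapse criteria", marked at 11 double-blind visits, including the telephone visits at Weeks 20 and 24. SAP 5.2.3 says that non-relapsers "will be censored at the time of the last applicable SAPS-H+D assessment". SAP 5.2.5 schedules that scale at the open-label visits "and at Weeks 13, 14, 16, 18, 22, 26, 30, 34, and 38 during the double-blind period", which is nine double-blind visits and neither of the calls.

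All seven sensitivity analyses in SAP 13.1.2 (four if the trial stops at the interim, three if not) use the last SAPS-H+D. The typical wording is "Subjects without any such relapse event will be censored at the last SAPS-H+D assessment prior to the study discontinuation date". In SAP 13.1.1, subjects who discontinue early "will have time to relapse values imputed conditionally on their observed censored values". Censoring through completion, sponsor termination or the interim data cut "will be treated as non-informative and no imputation will be performed for these subjects".

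**ESRS-A.** Protocol 9.5.4 lists the total and every subscale among the descriptive safety summaries. SAP 14.8.1 and 14.8.2 summarize the total and four single-item global ratings, which SAP 5.2.13 describes separately from the four subscales.

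**Declaration.** SAP 20 states that nothing deviates from the analyses in Protocol Amendment 1.

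**The concern.** Read literally, the two documents give different censoring dates for the primary endpoint, and so for the test that can stop the trial at the interim. The SAP's rule is also uneven. A relapse discovered at the Week 20 or Week 24 call counts as an event, while a call that finds no relapse adds no follow-up. No planned analysis applies the protocol's literal rule: the sensitivity analyses share the SAP's rule, and the imputation starts from the same censored times and leaves out subjects still ongoing at the interim.

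If the choice moved the hazard ratio or the boundary decision, an undeclared departure would leave room to dispute which rule governed. Separately, four safety summaries named in the protocol (subscales of 10, 6, 6 and 2 items) do not appear in the SAP's text.

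**Working it through.** **1. The plan's own figures.** Inputs from Protocol 9.3: 26-week relapse of 60% on placebo and 35% on pimavanserin, 25% dropout, two-sided alpha 0.05, 90% power.

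- HR = ln(0.65)/ln(0.40) = 0.470, as stated.
- Schoenfeld events = 4(1.960 + 1.282)²/(ln 0.470)² = 74. With 75 events at alpha 0.0479, power is 90.1%.
- Probability of relapse before dropout:
  - placebo: (0.9163/1.2040) × (1 − 0.40 × 0.75) = 0.533
  - pimavanserin: (0.4308/0.7185) × (1 − 0.65 × 0.75) = 0.307
- N = 75/0.420 = 178.6, against 178 stated.
- The O'Brien-Fleming boundaries at 38/75 come out at 0.0054 and 0.0479 two-sided, as stated.

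**2. Who is affected when everyone is followed to the end.** Completers have a SAPS-H+D at Week 38, so the two rules agree for them. The rules differ only for a dropout whose last relapse check was a call, meaning one who leaves in double-blind weeks 8-10 or 12-14. The gap is then 2 weeks. Take the worst case, in which no dropout has an early-termination SAPS-H+D, and let S(t) be the probability of still being at risk:

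- Placebo: (0.2877/1.2040) × [S(8) − S(10) + S(12) − S(14)] = 0.2389 × 0.1119 = 2.7%
- Pimavanserin: (0.2877/0.7185) × 0.0817 = 3.3%
- Out of 89 per arm, that is about 2.4 and 2.9 subjects.
- Mean follow-up is 26 × 0.70/1.2040 = 15.1 weeks on placebo and 26 × 0.5125/0.7185 = 18.5 weeks on pimavanserin.
- Time lost: placebo 2 × 0.0267/15.1 = 0.35%; pimavanserin 2 × 0.0327/18.5 = 0.35%.

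The loss is the same proportion in both arms, so a ratio of event rates does not move. If 70% of dropouts have an early-termination SAPS-H+D, the affected share falls to about 0.3 × 3.0% = 0.9%.

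**3. Interim and final, by simulation.** Assumed ranges: uniform accrual over 365 or 730 days; an early-termination SAPS-H+D in 0, 70 or 100% of dropouts; 0, 30 or 100% of relapses dated between visits.

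| | Interim, 38 events | Final, 178 fully followed | Final, stopped at 75th event |
|---|---|---|---|
| Subjects censored 14 days earlier | 4-10% | 0-3% | 2-4% (6-14 subjects) |
| Person-time lost | 0.6-1.7% | 0-0.4% | 0.2-0.5% |
| Trials where the rules disagree on the boundary | 0.2-1.1% | about 0.1% or fewer | 0.3% or fewer |

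The last column assumes planned randomization of 240-400 and 26-week placebo relapse of 32-50%, which leaves 32-68 subjects still ongoing. Of the affected subjects at the interim, 63-100% are ongoing rather than dropouts. Placebo 26-week Kaplan-Meier relapse at the interim is 0-0.5 points higher under the SAP's rule.

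One scenario in full (365 days, 70% with early-termination SAPS-H+D, all relapses between visits) gives an HR of 0.4686 against 0.4684 at the interim and 0.4691 under both rules at the final. In single trials of 178, the median absolute difference in interim HR is 0.1-0.7% and the 95th percentile 0.5-2.4%.

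**4. Operating characteristics.** Under HR 1 with 47.5% relapse in both arms, one-sided type I error is 2.45% under one rule and 2.44% under the other (16,000 trials). Power is 0.8945 against 0.8949 (8,000 trials).

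**5. ESRS-A.** 10 + 6 + 6 + 2 = 24 items scored 0-5, so the total runs 0-120 and the subscales 0-50, 0-30, 0-30 and 0-10. SAP 5.2 says that subscores are in general derived, and listed alongside the raw scores. SAP 1 places table specifications in a separate document. No hypothesis test uses any ESRS-A score.

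**The case for a change.** The strongest case for acting is that the relapse assessment is a named, scheduled procedure. Three of the four relapse criteria (another antipsychotic, stopping for lack of efficacy, hospitalization) need no SAPS-H+D and can be checked by telephone. The SAP reprints both schedule rows, so it cannot simply be defining one as the other. SAP 20 is categorical, and a declaration plus one extra Cox run would cost little. SAP 5.2.3 also points to 13.2.2 for the sensitivity censoring times when they are in 13.1.2, a clerical slip.

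The textual part stands: the dates can differ, and SAP 20 mentions neither difference. The consequence does not follow. SAP 5.2.3 fixes one rule in advance, so the analyst has no choice to make after seeing data, and Protocol 9.1 leaves methodological detail to the SAP. The last date on which all four criteria could be judged is a sound reading of when a subject was last known to be relapse-free. Dropouts with an early-termination visit have a SAPS-H+D at it. For those without, the imputation in SAP 13.1.1 runs onward from the censoring date and so covers the lost fortnight, though under the placebo hazard. Ongoing subjects at the interim are cut off administratively, and their shorter follow-up is already in the figures above.

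On ESRS-A, the argument that subscales would rescue scores lost when the total is missing has no missingness rate behind it. The four global ratings still give information by domain.

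**Conclusion.** The discrepancy is genuine but harmless. The SAP's rule is explicit, prespecified and reasonable. Against the protocol's literal wording it shifts the average hazard ratio by less than 0.1% and leaves type I error and power essentially where they were. A run under the literal rule would be confirmatory only. The missing ESRS-A subscale summaries are descriptive, can be produced from data already collected, and may already be in the table specifications. A line in SAP 20 would tidy the record, but no result or conclusion depends on it.

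The sizes rest on exponential relapse and dropout at the protocol's rates, visits on schedule, and the assumed ranges for accrual, early-termination SAPS-H+D and relapse dating. The simulated Cox model has treatment only, with Efron ties, and takes the interim at 38 events against a fixed one-sided 0.0027. The SAP adds strata covariates, robust variance and exact ties, cuts the data when the 38th adjudication is complete, and recalculates the boundary. The boundary-disagreement rates are therefore illustrative. Missed SAPS-H+D assessments, or unscheduled relapse checks without one, could widen the gap for individual subjects.
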